7.5.5 Subgroup Analysis

All analyses described in this section will be performed on the ITT Analysis Population. Table 7.5.5-1 shows the subgroups of interest for analyses of the primary efficacy endpoint of renal response. If the value of the grouping variable cannot be determined for a subject, the subject will be excluded from the corresponding subgroup analysis. Only subgroups consisting of 10% or more of the total study population will be considered.

Table 7.5.5-1: Subgroup of Interest of the Primary Efficacy Assessment of Renal Response

Subgroup Factor	Categories
APOL1	High Risk
	Other
Age	Pediatric (< 18 years)
	Adult (≥ 18 years)
Gender	Male
	Female
Race	Caucasian
	Black
	Asian
	Others
Baseline UPCR	Baseline UPCR < 6mg/mg
	6mg/mg ≤ Baseline UPCR < 9mg/mg
	Baseline UPCR ≥ 9mg/mg
Diagnosis	FSGS
	MCD

The proportion of subjects who achieve renal response, defined by composite renal index, at Day 113 at the end of double-blind period in abatacept and placebo arm will be summarized using point estimates and 95% confidence interval for each treatment group by subgroup. The difference in proportions between treatment groups for each subgroup will be provided by point estimate and 2-

sided 95% confidence interval using normal approximation, without any adjustments for strata, if the number of events in each individual treatment group is at least 5. Otherwise, confidence intervals using an exact method will be provided.

7.6 Safety

Analysis of all safety data will follow the BMS standard safety data conventions and supplements to the standard conventions for the abatacept programs⁵.

The evaluation of drug safety is based primarily on clinical AEs, vital signs and laboratory abnormalities reported during the study. All safety presentation will be based on the As Treated Analysis Population by treatment group. Unless otherwise specified adverse events and laboratory abnormalities will be summarized for double-blind period, cumulative abatacept safety period and OLE period as described in [APPENDIX 2](#). The definition of each period is provided in [Section 6.1](#).

Frequency and individual listings of all AEs will be generated. Changes in clinical laboratory test results from baseline will be summarized. Laboratory marked abnormality using pre-defined abnormality criteria will also be descriptively summarized. There will be no statistical testing of group difference with respect to frequencies of AEs or laboratory marked abnormalities.

7.6.1 Adverse Events

Adverse events are recorded by the investigators on the Serious and Non-Serious Adverse Event page(s) of the CRF. All investigators are required to report the nature, the onset and resolution date, intensity, action taken, treatment required for event, and to express their opinion regarding the relationship between the AE and the study medication.

All AEs are coded and grouped into Preferred Terms (PT) by System Organ Class (SOC), using the Medical Dictionary for Regulatory Activities (MedDRA). Listings and summaries will be based on the resulting SOCs and PTs.

All reported AEs and SAEs will be listed, indicating the subject ID, treatment group, age, gender, race, day of onset relative to start of dosing, resolution date, investigator-assessment of relationship to study drug, investigator-assessment of intensity of event, action taken regarding study drug and whether treatment was required for the event.

All adverse events with an outcome of death will be listed.

Selected AE summaries will be generated for the double-blind period and cumulative abatacept safety period which include SAEs, AEs leading to study drug discontinuation, most common related AEs (reported in at least 2% of subjects) and most common (serious or non-serious) AEs (reported in at least 5% of subjects).

AE summaries by age group (adults versus pediatrics) will be presented for serious AEs, AEs leading to study drug discontinuation, most common related AEs (reported in at least 2% of subjects in any treatment group for each age group separately).

Summary information (the number and percent of subjects) regarding AEs (for serious or non-serious events) will be tabulated by SOC, PT and treatment group for:

- Serious adverse events (SAE).
- AEs leading to study drug discontinuation.
- AEs related to study drug.
- Related events categorized by intensity.
- Most common related AEs (reported in at least 2% of subjects in any treatment group).
- AEs by intensity.
- All AEs (serious or non-serious).
- Most common (serious or non-serious) AEs (reported in at least 5% of subjects in any treatment group).
- Serious adverse events and related serious adverse events with death as an outcome following EudraCT requirements.

Laboratory AEs are laboratory results identified by the Investigator as AEs and thus reported on the AE pages of the CRF. Any such AE will be included in the respective AE summaries.

7.6.2 Adverse Events of Interest

7.6.2.1 Renal Related Events

All reported renal-related events during treatment will be summarized by preferred term and treatment group. Renal-related events will be defined using the MedDRA Maintenance and Support Services Organization (MSSO) Chronic Kidney Disease Structured MedDRA Query (SMQ), MSSO Embolic and Thrombotic Disease SMQ, and BMS custom Renal Supplement SMQ. The listing will include all renal-related events up to the database lock.

7.6.2.2 Infections

All reported infections and infestations within the SOC: Infections and infestations occurring during treatment will be summarized by preferred term and treatment group. The listing will include all reported infections and infestations up to the database lock. Summary of infections and infestations AEs by intensity will also be summarized. A Kaplan-Meier plot of time to first serious infection during treatment will also be presented by treatment group.

In addition to the SOC of infections and infestations, all events in the cSMQ of Opportunistic Infections will be summarized by preferred term and treatment group. The listing will include all reported events up to the database lock.

7.6.2.3 Malignancy

All events in the MSSO malignancies SMQ list will be summarized. These events will be summarized by preferred term and treatment group. The listing will include all reported events up to the database lock.

7.6.2.4 Autoimmune Disorders

The frequency of pre-specified autoimmune disorders, defined using a BMS custom Autoimmune Disorder SMQ will be provided. Autoimmune disorders will also be summarized by intensity. All reported autoimmune disorders reported up to the database lock will be listed.

7.6.2.5 Infusional Reactions

- 1) Peri-infusional AEs of interest are defined as those AEs occurring within the first 24 hours after the start of each study drug infusion that are included in the pre-specified MedDRA list of peri-infusional events of interest.
- 2) Acute infusional AEs of interest are defined as those AEs occurring within the first hour after the start of each study drug infusion that are included in the pre-specified MedDRA list of peri-infusional events of interest.

The pre-specified MedDRA code of peri-infusional AEs of interest will be provided prior to database lock and will be included in the CSR.

- 3) Other peri-infusional AEs are defined as other AEs occurring during the first 24 hours after the start of each study drug infusion but not included in the pre-specified list of peri-infusional AEs defined in 1) above.

The number and percent of subjects experiencing the infusional AEs defined in 1) above through 3) above will be summarized by SOC, PT and treatment group. The distribution of the infusional AEs of interest by intensity will also be provided except for the AEs defined in C above. All reported peri-infusional AEs of interest reported up to the database lock will be listed.

7.6.3 Incidence Rate Analyses

Incidence rate is defined as the quotient of number of subjects with event and exposure (patient-years), where the exposure (patient-years) is the sum over all subjects' exposure during a pre-specified study period (censored at the time of the first occurrence of event) divided by 365. The resulting incidence rate is multiplied by 100 to express the rate per 100 p-y. Incidence rates per 100 p-y and associated 95% Poisson confidence intervals will be calculated for each treatment group.

Incidence rate analyses will be performed for SAEs, Renal Related AEs, Opportunistic Infections, Malignancy and Autoimmune disorders, the point estimate and 95% CI of incidence rate (per 100 patient-years) of each endpoint will be provided by system organ class and preferred term, separately for each treatment group.

The analyses will be performed for events that occurred in double-blind period up to 56 days post last dose in double-blind period or first dose date in OLE whichever is earlier.

For subjects who completed Period 1 and entered Period 2 prior to Protocol Amendment 2, the analyses will be performed for events that occurred in Period 1 up to the first dose in Period 2.

7.6.4 Multiple Adverse Events

Several descriptive summaries of adverse events that takes into account the number of occurrences that an AE was reported by individual patients will be provided. In order to prepare these summaries, the CRF data will be processed according to standard BMS algorithms to categorize each line of patient data as a new occurrence or a continuation of an existing event. This determination will be based upon onset and resolution dates. Each line of patient data will represent the maximum severity observed as well as the last known assessed relationship to study medication by the investigator.

This data will be presented as the rate per 100 years of patient exposure. Exposure to study medication will be calculated according to approved standard BMS algorithms as well.

As an example, if 5 patients report 7 unique episodes of headache and had a combined cumulative exposure of 20 years to study medication, the incidence rate is reported as $7/20 * (100)$ or 35 cases per 100 patient years of exposure.

For adverse events with multiple occurrences, the following will be provided:

- A table showing the total number and rate (exposure adjusted) of occurrences for general AEs occurring in at least 5% of the subjects treated. AEs will be organized by System Organ Class (SOC) and Preferred Term (PT), and reported by and treatment group.
- A listing displaying the unique instances of all AEs (i.e., after duplicates have been eliminated and overlapping and contiguous occurrences of the same event have been collapsed).

No formal comparisons are made between treatments. No formal statistical testing will be performed, only summary statistics of adverse events with multiple occurrences for double-blind period, cumulative abatacept safety period and OLE period as described in [APPENDIX 2](#) will be provided.

7.6.4.1 EudraCT Summaries

Exposure adjusted adverse event summaries including multiple occurrences of unique adverse events for EudraCT reporting requirements will be presented by treatment group in the cumulative abatacept safety period. These summaries include serious adverse events, drug related serious adverse events and non-serious adverse events using a global cutoff of 5 percent.

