6 STUDY PERIODS, TREATMENT REGIMENS AND POPULATIONS FOR ANALYSES

6.1 Study Periods

In this study, there are four study periods: screening period, double-blind period (DB), open label extension period (OLE), and follow-up period.

The following analysis periods defined below are for analysis purposes. The definitions below indicate the data to be included in the analysis of each specified period. Subjects discontinued during a specified period (DB or OLE) will be considered on-treatment for 56 and 42 days after the last dosing in that period for safety and efficacy analysis respectively. Follow-up period data will be included in one of the analysis periods depending on the time of completing the study.

Screening Period: Starts with the day of enrolment and ends prior or on the day of first dose of study medication (abatacept or placebo).

Double-Blind Period: Starts with the first dosing of double-blind study medication and ends 56/42 days (for safety/efficacy analysis) after the last dose of the double-blind period or the first dosing of OLE, whichever is earlier.

For subjects who completed Period 1 and entered Period 2 prior to Protocol Amendment 2, includes data from first dose date in Period 1 up to the first dose in Period 2.

Open Label Extension Period (OLE): Starts with the first dosing in the OLE and ends 56/42 (for safety/efficacy analysis) days after the last dose in the OLE.

Cumulative Abatacept Safety Period: Starts at the time of the first dose of abatacept (either in the double-blind period for the subjects randomized to abatacept or in the OLE for the subjects randomized to placebo) and continues up to 56 days post last dose of abatacept for safety (AE and laboratory summaries). The last abatacept dose can be last dose in double-blind period for subjects not treated in the OLE.

For subjects who completed Period 1 and entered Period 2 prior to the protocol revision:

- For subjects on abatacept during Period 1:
 - For subjects who do not enter OLE period: starts with the first dosing of Period 1 and ends 56 days after the last dosing of Period 1.
 - For subjects who enter OLE period: starts with the first dosing of Period 1 and ends 56 days after the last dosing of Period 1 combined with OLE period that starts with the first dosing in the OLE period and ends 56 days after the last dosing in the OLE period.
- For subjects on placebo during Period 1:

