 - For subjects who do not enter OLE period: starts with the first dosing of Period 2 and ends 56 days after the last dosing of Period 2.
 - For subjects who enter OLE period: starts with the first dosing of Period 2 and ends 56 days after the last dosing of OLE period. If a subject's first dosing in OLE period is more than 56 days from last dosing in Period 2, the duration after 56 days from last dosing in Period 2 to the first dosing in OLE will be excluded.

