7.4 Extent of Exposure

7.4.1 Study Therapy

Extent of exposure to double-blind study drug will be summarized using the As Treated Analysis Population in two ways:

- Number of infusions.
- Number of days a subject is known to be on study drug ignoring dosing interruptions.

The number of infusions subjects received will be based on the study medication page of the CRF when an infusion date is present.

The number of days the subject is known to be on study drug (exposure to study drug) during each period is calculated as:

Double-blind period:

- Discontinued subjects during double-blind period and subjects completed double-blind period but do not continue into the OLE:

Exposure in days = (date of last study medication in the double-blind period - date of first study medication in the double-blind period + 1) + 56.

- Subjects continuing in the OLE:

Exposure in days = (date of first study medication in OLE - date of first study medication in double-blind period) - adjustment.

Adjustment is the period after 56 days from last study medication from double-blind period to the first study medication in OLE.

- Subjects who completed Period 1 and entered Period 2 prior to the protocol revision:

Exposure = (date of first study medication in Period 2 - date of first study medication in Period 1) - adjustment.

Adjustment is the period after 56 days from last study medication from Period 1 to the first study medication in Period 2.

OLE period:

Exposure = (date of last study medication in OLE - date of first study medication in OLE + 1) + 56.

Cumulative abatacept safety period:

- Subjects treated with abatacept and discontinuing before entering the OLE:

Exposure in double-blind period = (date of last study medication in double-blind period - date of first study medication in double-blind period + 1) + 56.

- Subjects treated with abatacept and continuing in the OLE, it is the sum of the following:

Exposure in double-blind period = (date of first study medication in OLE - date of first study medication in double-blind period) - adjustment.

Exposure in OLE = (date of last study medication in OLE - date of first study medication in OLE + 1) + 56.

For subjects randomized to placebo, the date of first abatacept study medication is the date of first study medication in OLE. For subjects randomized to abatacept, the date of first abatacept study medication is the date of first double-blind period.

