APPENDIX 3 CLINICAL REPORTS CONTENT

Table 9-2: Safety Analysis by Period

	End of Double-Blind	End of Study	
	Period CSR	CSR	
	Double-Blind Period	Cumulative Abatacept Safety Period	OLE Period
Serious Adverse Events	X	X	X
AEs leading to study drug discontinuation	X	X	X
AEs related to study drug	X	X	X
Related events categorized by intensity	X	X	X
Most common related AEs (reported in at least 2% of subjects in any treatment group)	X	X	X
All AEs (serious or non-serious)	X	X	X
AEs by intensity	X	X	X
Most common (serious or non-serious) AEs (reported in at least 5% of subjects in any treatment group)	X	X	X
Serious adverse events and related serious adverse events with death as an outcome (EudraCT)		X	
AEs of Special Interest (Renal Related Events, Infections, Malignancy, Autoimmune Disorder, Infusional Reactions)	X	X	
Multiple Adverse Events	X	X	
EudraCT summaries - Exposure adjusted summaries		X	
Laboratory abnormalities	X	X	X
Laboratory Shift Tables	X	X	X
Mean Change from Baseline in Lab Parameters	X		
Vital Signs	X		X
Immunogenicity	X	X

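### The EudraCT adverse-event summaries are planned by treatment group but only for the cumulative abatacept safety period, so they leave out the placebo arm's double-blind events

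*SAP*

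**What the plan says.** SAP 7.6.4.1 covers serious adverse events, drug-related serious adverse events and non-serious adverse events at a 5% cutoff. It states that these summaries "will be presented by treatment group in the cumulative abatacept safety period". Section 9 repeats the cumulative basis for them.

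Table 9-2 (SAP Appendix 3) has two EudraCT rows: "EudraCT summaries - Exposure adjusted summaries", and the fatal-event row that begins "Serious adverse events and related serious adverse events with death as an outcome (EudraCT". Each carries one mark, under the cumulative period; the double-blind column is empty. SAP 7.6.1 also lists the fatal-event table by treatment group, without naming a period.

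SAP 6.1 starts the cumulative period at the first abatacept dose, "either in the double-blind period for the subjects randomized to abatacept or in the OLE for the subjects randomized to placebo". SAP 7.4.1 applies the same rule to exposure: "For subjects randomized to placebo, the date of first abatacept study medication is the date of first study medication in OLE".

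Subjects who entered the old Period 2 before Amendment 2 have their own windows in SAP 6.1:
- Placebo first, then OLE: the window "starts with the first dosing of Period 2 and ends 56 days after the last dosing of OLE period".
- Abatacept first: the window "starts with the first dosing of Period 1 and ends 56 days after the last dosing of Period 1", with the OLE window added for those who enter it.

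SAP 6.2 defines two treatment groups only, abatacept IV and placebo IV. SAP 7.6 bases safety presentations on the As-Treated population by treatment group. SAP 6.3.2 groups that population by randomized treatment, unless a subject received the other treatment throughout the double-blind period.

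**The concern.** A period defined by abatacept exposure does not fit a table split into abatacept and placebo. On the SAP's own group definitions, the placebo column would contain only time on abatacept, collected over a later and shorter window than the abatacept column. If the table is instead read as abatacept only, it has no control. On either reading, a serious or fatal event on double-blind placebo in the placebo arm does not enter the EudraCT tables.

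The stake is how those tables are read. Protocol 1.5 describes a population already at significant risk of infection, end-stage renal disease and death, and names infection as the major identified risk of abatacept. Without the placebo rate, a reader of these tables cannot separate drug harm from background disease. A placebo heading over abatacept events would mislead.

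**Working it through.** **The plan's own figure.** SAP 7.6.4 gives a worked rate: 7 episodes in 20 years of exposure. 7/20 × 100 = 35 per 100 patient-years, as stated. The rate formula is sound; the question is which time and events enter it.

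**Scope, side by side.**
- EudraCT summaries: cumulative period only (7.6.4.1, Section 9, Table 9-2).
- Other multiple-occurrence summaries: double-blind, cumulative and OLE periods in the text of 7.6.4; Table 9-2 marks double-blind and cumulative.
- Incidence rates (7.6.3): double-blind period, by treatment group.

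Of these exposure-based summaries, only the EudraCT set omits the double-blind period. No reason is given.

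**Inputs.**
- 90 subjects randomized 1:1, so 45 per arm (SAP 5).
- Double-blind doses on Days 1, 15, 29, 57 and 85 (SAP 2.1).
- OLE Day 1 is double-blind Day 113 (Protocol 3.1.3); last OLE dose on OLE Day 141 (Protocol 4.5.3).
- Exposure formulas with the 56-day offset (SAP 7.4.1); division by 365 (SAP 7.6.3).

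**Days per subject dosed on schedule.**
- Double-blind, enters the OLE: 113 − 1 = 112. No adjustment applies, because 85 + 56 = 141 is later than Day 113.
- Double-blind, does not enter: (85 − 1 + 1) + 56 = 141.
- OLE: (141 − 1 + 1) + 56 = 197.
- Cumulative period, abatacept arm entering the OLE: 112 + 197 = 309.
- Cumulative period, placebo arm entering the OLE: 197, all on abatacept.

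**Placebo exposure left out.**
- All enter: 45 × 112/365 = 13.8 patient-years.
- None enter: 45 × 141/365 = 17.4 patient-years.

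OLE uptake is not in the documents. The table assumes full double-blind dosing, full OLE dosing by those who enter, and the same uptake in both arms.

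| Assumed OLE entry | Placebo subjects absent | Double-blind placebo patient-years left out | Cumulative patient-years, placebo-randomized | Cumulative patient-years, abatacept-randomized |
|---|---|---|---|---|
| 100% | 0 | 13.8 | 45 × 197/365 = 24.3 | 45 × 309/365 = 38.1 |
| 80% | 9 | (36 × 112 + 9 × 141)/365 = 14.5 | 36 × 197/365 = 19.4 | (36 × 309 + 9 × 141)/365 = 34.0 |
| 60% | 18 | (27 × 112 + 18 × 141)/365 = 15.2 | 27 × 197/365 = 14.6 | (27 × 309 + 18 × 141)/365 = 29.8 |
| 0% | 45 | 17.4 | 0 | 17.4 |

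Early discontinuation or early escape would lower these figures. For example, a child who enters the OLE on Day 85 has 85 − 1 = 84 double-blind days.

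**Subjects who entered Period 2.** For abatacept-first subjects the window runs to Day 85 + 56 = Day 141. If Period 2 dosing began on Day 113, 141 − 113 = 28 days of Period 2 placebo can fall inside it. For placebo-first subjects the window includes blinded Period 2 abatacept. The number of such subjects is not given.

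**The case against.** The strongest reply is that the randomized harm comparison is already planned. Table 9-2 marks the double-blind period for serious events, events leading to discontinuation, related events, all events, common events, events of special interest and multiple events. SAP 7.6.3 adds incidence rates with Poisson intervals by arm. SAP 7.6.2 covers embolic and thrombotic events within the renal-related set and plots time to first serious infection by arm. SAP 7.6.1 lists all events with a fatal outcome. All of this stands. A reader might infer that the trial reports no placebo comparison for harms; the documents do not support that.

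Two other strong readings also fail. One is that all blinded placebo time is excluded: up to about 28 days of Period 2 placebo in abatacept-first subjects can be included. The other is that the placebo-randomized group shows only open-label events: placebo-first subjects who entered Period 2 also contribute events on blinded abatacept.

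It can also be said that exposure adjustment deals with unequal windows, and that SAP 7.6.4 makes no formal comparison. Adjustment does help with length. It does not bring placebo events into the table, nor correct a placebo heading over abatacept events.

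Finally, the documents mention EudraCT requirements without stating them, and they do not rule out using the double-blind tables for the posting. So no breach of a registry rule can be claimed. The mismatch inside the SAP remains.

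**Conclusion.** The point holds for the EudraCT output and goes no further. As written, those tables omit the placebo-randomized group's double-blind events and every placebo subject who never takes abatacept. They would either place abatacept-exposure events under a placebo heading or show abatacept without a control.

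The exposure left out is about 13.8 to 17.4 patient-years. Both ends assume 45 placebo subjects dosed on schedule and differ only in OLE entry. On that schedule, with full OLE entry, the omitted time is 112/309 = 36% of a placebo-randomized subject's time across both periods. A reader might take this as 36% of the events, but that needs a constant event rate, which nothing in the documents supports. No efficacy analysis and no double-blind safety table is affected.

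**What to change.** Make the same change in SAP 7.6.4.1, Section 9 and both EudraCT rows of Table 9-2:

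- Add the double-blind period, by As-Treated arm (abatacept and placebo), using the double-blind safety window of SAP 6.1. If all subjects enter the OLE on schedule, each arm then contributes 13.8 patient-years over the same 112 days.
- Show the cumulative abatacept safety period as a single abatacept column. If it is split, label the columns by sequence (abatacept-abatacept, placebo-abatacept) and not by treatment group.

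The cost is SAP wording and a rerun of existing table programs on the double-blind period. No new data are needed. The only downside is a few extra tables.
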